12.2. SERIOUS ADVERSE EVENTS AND SUSPECTED UNEXPECTED SERIOUS ADVERSE REACTIONS

12.2.1. Definitions

12.2.1.1. Serious Adverse Event Definition

In addition to severity and causality ratings, each AE is to be classified by the investigator as “serious” or “not serious.”

An SAE is any untoward medical occurrence that:

- Results in death
- Is life-threatening

Note: The term “life-threatening” here refers to an event in which the subject was at risk of death at the time of the event. It does not refer to an event which hypothetically might have caused death if it were more severe.

- Requires inpatient hospitalization or prolongation of an existing hospitalization

Note: Hospitalization for an elective procedure, for a routinely scheduled treatment, or scheduled in advance of trial participation are not considered SAEs.

- Results in persistent or significant disability/incapacity, or disruption of the ability to conduct normal life functions
- Is a congenital anomaly/birth defect

Note: This applies if a subject exposed to an investigational product gives birth to a child with a congenital anomaly or birth defect.

- Is an important medical event

Important medical events that may not result in death, be life threatening, or require hospitalization may be considered serious when, based upon appropriate medical judgement, they may jeopardize the subject or may require intervention to prevent one of the outcomes listed in this definition.

Events **not** considered to be SAEs are hospitalizations for:

- Routine treatment or monitoring of the investigational product or indication under study not associated with any deterioration in condition

- Treatment that was elective or planned prior to enrollment for a pre-existing condition unrelated to the investigational product or indication under study that has not worsened
- Admission to a hospital for general care not associated with any deterioration in condition
- Treatment on an emergency outpatient basis for an event not fulfilling any of the definitions of serious given above and not resulting in hospital admission

Suspected Unexpected Serious Adverse Reaction Definition

A suspected unexpected serious adverse reaction (SUSAR) is any AE for which there is evidence to suggest a causal relationship between the drug and the AE, and which is assessed as both unexpected and serious. A suspected adverse reaction is considered “unexpected” if it is not listed in the Investigator’s Brochure or Reference Safety Information as associated with TransCon hGH, or if it is not listed at the specificity or severity that has been observed. The final determination of expectedness will be assessed by the Sponsor.

Non-Serious Adverse Events Leading to Discontinuation

If situation permits, non-serious events (including laboratory abnormalities and pregnancies) that may require permanent discontinuation of investigational product should be discussed with the Medical Expert prior to making any final decision.

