12. ADVERSE EVENTS, SERIOUS ADVERSE EVENTS, AND REPORTING

12.1. ADVERSE EVENTS

12.1.1. Definition

An AE is defined as any untoward medical occurrence in a clinical investigation subject administered a pharmaceutical product and which does not necessarily have a causal relationship with the treatment. An AE can therefore be any unfavorable and unintended sign, symptom, or

disease temporally associated with the use of a medicinal (investigational) product, whether or not related to that product. An AE can arise with any use (eg, in combination with another drug), route of administration, formulation, or dose, including an overdose.

Possible AEs associated with TransCon hGH are listed in the Investigator's Brochure or the accompanying Reference Safety Information. The adverse reactions associated with commercially available daily hGH-containing products that may or may not be observed with use of TransCon hGH are:

- Sudden death in pediatric patients with Prader-Willi syndrome; risk factors include morbid obesity, history of upper airway obstruction or sleep apnea, and unidentified respiratory infection
- Intracranial tumors, particularly meningiomas, in teenagers/young adults treated with brain irradiation as children
- Injection site reactions/rashes (as well as rare, generalized hypersensitivity reactions)
- Skin atrophy and lipoatrophy
- **Note:** Rotating the injection site (see Section 9.3) is expected to decrease the risk of skin atrophy or lipoatrophy.
- Headaches
- Glucose intolerance, including impaired glucose tolerance/impaired fasting glucose as well as overt diabetes mellitus
- Intracranial hypertension with papilledema, visual changes, headache, nausea, and/or vomiting
- Fluid retention manifested by edema, arthralgia, myalgia, nerve compression syndromes (including carpal tunnel syndrome/paresthesias)
- Hypothyroidism (central [secondary] hypothyroidism may first become clinically evident or worsen in patients with GHD during hGH treatment)
- Slipped capital femoral epiphysis (occurs more frequently in patients with endocrine disorders or in patients undergoing rapid growth)
- **Note:** Any subject with the onset of a limp or complaints of hip or knee pain should be carefully evaluated for a slipped capital femoral epiphysis.
- Progression of pre-existing scoliosis due to rapid growth (hGH has not been shown to increase the occurrence of scoliosis)

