Any change from baseline health status that meets the above AE definition and occurs from the time of the first administration of investigational product until the completion of the study or the Early Termination Visit will be recorded as an AE.

Out-of-range laboratory values or test results may constitute AEs if they:

- induce a new/worsening diagnosis, clinical sign, or symptom, or
- require therapy.

Routine titration of chronic, concomitant medications (eg, increase of levothyroxine dose due to interval weight gain and without associated signs/symptoms of overt hypothyroidism) would not be considered as AEs. Whenever possible, an AE should be recorded as a specific diagnosis or syndrome rather than as a sign, symptom, or out-of-range laboratory value. If there is not a diagnosis, the event term should be the clinical sign or symptom. Based on an investigator’s clinical judgement, multiple concurrent symptoms should be grouped together as a single, unifying diagnosis (e.g. headache, fever, cough, and coryza constitute a probable viral upper respiratory tract infection, and this single AE term is more appropriate than listing each symptom as a separate AE).

Care should also be taken to record the most medically appropriate term (eg, hypertension for elevated blood pressure that persists and requires chronic treatment and follow-up, or increased blood pressure for elevated blood pressure that occurs for a limited time and does not persist or require ongoing treatment).

AEs will be documented at the maximum intensity experienced. If a previously recorded AE or condition recorded as part of medical history increases in severity or frequency, it will be recorded as a new AE.

All AEs will be considered ongoing until they have completely resolved or, in the case of a condition recorded as part of medical history, returned to baseline status prior to investigational product administration. At study completion or the Early Termination Visit, all AEs should have a statement regarding resolution.

Any SAE that is determined to be related to the investigational product will be followed until resolution or stabilization.

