12.2.2. Reporting

All initial and follow-up information regarding SAEs or SUSARs must be reported by the investigator to the Sponsor or its representatives within 24 hours of discovery, including those related to protocol-mandated procedures and regardless of suspected causality. Reporting must not be delayed by waiting for additional information. The minimum information required for reporting an SAE are the AE term (diagnosis) and the investigator’s initial causality assessment. Additional information can be reported to the Sponsor or its representatives as a follow-up report.

The Sponsor (or its representatives) is responsible for reporting within the time frame required by applicable regulations all SUSARs to:

- Investigators
- Central IRBs/HRECs/IECs
- National ethics committees (if applicable)
- Appropriate regulatory authorities

It is the investigators’ responsibility to comply with the requirements of their local IRB/HREC/IEC for reporting SUSARs, other SAEs, and any new and/or relevant safety information provided by the Sponsor or its representatives. At minimum, SUSARs must be brought to the attention of these review boards in accordance with regional regulations.

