14.2. SAMPLE SIZE DETERMINATION

This trial is intended to assess long-term safety and efficacy in support of market approval. All subjects who have completed a prior phase 3 TransCon hGH trial, have not permanently discontinued investigational product, and meet eligibility criteria will be invited to participate. The sample size is determined by the prior trial sizes.

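### Protocol 12.2.1.1 excludes elective and scheduled admissions from SAEs under two inconsistent rules, and does not say which governs

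*Protocol*

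**What the plan says.** Protocol section 12.2.1.1 lists the criteria that make an event serious. One of them is that it "Requires inpatient hospitalization or prolongation of an existing hospitalization". The Note directly beneath reads: "Hospitalization for an elective procedure, for a routinely scheduled treatment, or scheduled in advance of trial participation are not considered SAEs".

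Further down, the same section lists hospitalizations that are not SAEs. Two of its four bullets cover the same ground as the Note, but with conditions:

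- on routine care, the wording is "Routine treatment or monitoring of the investigational product or indication under study not associated with any deterioration in condition";
- on elective or planned care, the exclusion covers what is "elective or planned prior to enrollment for a pre-existing condition unrelated to the investigational product or indication under study that has not worsened".

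The other two bullets concern general care without deterioration, and emergency outpatient treatment that does not lead to admission. Nothing in the section ranks the Note against the list.

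Three other places bear on the point. Section 12.1.3 says that if a "condition recorded as part of medical history increases in severity or frequency, it will be recorded as a new AE". Section 12.2.2 says that SAE information "must be reported by the investigator to the Sponsor or its representatives within 24 hours of discovery", whatever the suspected cause. SAP section 8.1 repeats the hospitalization criterion with neither exclusion attached, and plans a summary and a listing of serious TEAEs.

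**The concern.** Long-term safety is the primary objective, and the serious-TEAE table is one of its main outputs. Whether an event enters that table is decided site by site, at about 100 sites, from section 12.2.1.1. If the section gives two exclusion rules of different width, two investigators can classify the same admission differently and each can point to the protocol.

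The admissions affected are planned ones, and some recognised growth hormone risks develop slowly enough to be treated that way. Section 12.1.1 names "Progression of pre-existing scoliosis due to rapid growth" among the reactions associated with daily hGH products. A planned operation for such progression shows where the two rules part.

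More than a table is involved. The serious flag starts the 24-hour report. An event must also be serious before it can be a SUSAR, so a related and unexpected event classed as non-serious cannot become one.

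**Working it through.** No arithmetic applies. The check is to set the two rules side by side and run the same cases through both. Every case is an inpatient admission that is elective, routine or scheduled in advance, with hospitalization the only seriousness criterion met. Where the list does not exclude a case, the general criterion applies and the event is serious.

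| Case | Note | List | Same answer? |
|---|---|---|---|
| 1. Condition pre-existing, unrelated, not worse | not SAE | not SAE | yes |
| 2. Condition pre-existing but worse | not SAE | not excluded, so SAE | no |
| 3. Elective procedure for a condition new since enrolment | not SAE | not excluded, so SAE | no |
| 4. Condition related to the product | not SAE | not excluded, so SAE | no |
| 5. Condition related to the indication | not SAE | SAE, unless routine and without deterioration | no, apart from that exception |
| 6. Routine scheduled treatment, with deterioration | not SAE | not excluded, so SAE | no |

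The rules agree where the list's own conditions are met and differ elsewhere.

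The scoliosis example follows case 2. Progression of a medical-history condition is a new AE under section 12.1.3, so the investigator must decide whether it is serious. Under the Note, planned surgery does not count as a qualifying hospitalization. Under the list, the condition has worsened, so the exclusion does not apply.

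Four limits on the comparison:

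- Unplanned admissions are outside the Note and are treated alike under both texts.
- Case 3 can arise only through the Note's elective or routine-treatment wording. A condition that is new since enrolment cannot have had its admission booked before the trial.
- An event that is serious on another ground is serious under either rule.
- Adding the Note to the list can only remove events from the serious count, so the direction is known.

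The number of such admissions is not known. The documents give no rate of elective admissions and no expected serious-event rate, and "The sample size is determined by the prior trial sizes", so there is no planning assumption to borrow.

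**The case against.** The strongest reply is that both texts are exclusions. The list does not say that whatever falls outside it is serious, so a reader might apply both exclusions cumulatively. The Note would then settle every elective or scheduled case and no two sentences would command opposite answers. It is right that the list classifies nothing as serious by itself; the general criterion does that. But on the cumulative reading the requirements of pre-existence, unrelatedness and no worsening do no work for elective or pre-booked admissions. The section remains inconsistent.

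A second reply is that other criteria would catch the important cases. Surgery for progressing scoliosis could qualify as a disruption of normal life functions or as an important medical event. This stands in part and narrows the point to events where hospitalization is the sole criterion met. The important-medical-event route rests on individual judgement, so it does not replace a clear rule.

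A third reply is that the event is not lost. This stands. Only AEs that are both mild and unrelated may be left off the CRF, so progression needing surgery would normally appear in the TEAE tables by intensity and relationship. The Medical Expert, the sponsor and the independent safety committee also review safety data. What depends on the text applied is the serious flag and what follows from it.

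A reader might also infer that the extension design makes the problem much larger. Most of the children were already on TransCon hGH in a parent trial, so admissions booked for problems that arose on the drug would fall under the Note's exclusion of those arranged beforehand. The documents do not support this as an effect on the planned table. SAP section 8.1 counts only AEs that first occurred or worsened after the first extension dose, so a parent-trial problem that has not worsened is outside the serious-TEAE table under either rule. The number of children with prior exposure also says nothing about how many had an admission booked.

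**Conclusion.** The inconsistency is real and can be verified from one section of the protocol. For elective or scheduled admissions with no other seriousness criterion met, the serious flag, the 24-hour report, possible SUSAR status and entry in the serious-TEAE table turn on which text the site applies when the condition is new, worsened or related to the product. The Note can only lower the count. The SAP does not resolve it.

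The size is unknown. A reader might be inclined to guess a percentage of children with such admissions and compare it with the standard error of a guessed serious-event rate. Neither figure is in the documents, so the result would carry no information. The conclusion rests on the wording alone, and on the assumption that at least some sites will follow the Note and others the list. It does not show that any event has been misclassified, or that AEs are going unrecorded.

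**What to change.** Replace the Note with a cross-reference to the list of hospitalizations not considered SAEs later in section 12.2.1.1, and leave that list's bullets as they stand. One conditional exclusion then applies. No further test, such as an overnight stay or a new reference date, should be added: it would create a third rule and could conflict with the bullets on routine and general care.

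Tell sites which rule governs. Before database lock, check AEs already recorded as non-serious that involved an elective or scheduled inpatient admission against it.

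The cost is one sentence in a protocol amendment with the usual approvals, a site communication, and a data query limited to those AEs but spread over about 100 sites. Expect a few more SAE reports and a slightly higher serious-TEAE rate.

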12.2.2. Reporting

All initial and follow-up information regarding SAEs or SUSARs must be reported by the investigator to the Sponsor or its representatives within 24 hours of discovery, including those related to protocol-mandated procedures and regardless of suspected causality. Reporting must not be delayed by waiting for additional information. The minimum information required for reporting an SAE are the AE term (diagnosis) and the investigator’s initial causality assessment. Additional information can be reported to the Sponsor or its representatives as a follow-up report.

The Sponsor (or its representatives) is responsible for reporting within the time frame required by applicable regulations all SUSARs to:

- Investigators
- Central IRBs/HRECs/IECs
- National ethics committees (if applicable)
- Appropriate regulatory authorities

It is the investigators’ responsibility to comply with the requirements of their local IRB/HREC/IEC for reporting SUSARs, other SAEs, and any new and/or relevant safety information provided by the Sponsor or its representatives. At minimum, SUSARs must be brought to the attention of these review boards in accordance with regional regulations.

13. SAFETY MONITORING

The Sponsor will conduct an ongoing review of all trial data, with particular attention given to laboratory findings, AEs, and concomitant medications. Any important safety trends or other findings considered related to the investigational product will be reported to the investigators and to regulatory authorities. In particular, the Sponsor will notify investigators and regulatory authorities of AEs that:

- Fulfill the criteria for SUSARs
- Occur at a meaningfully greater frequency than described in the current Investigator's Brochure or Reference Safety Information

14. STATISTICS

The Statistical Analysis Plan (SAP) will provide a detailed description of the planned statistical analyses. If discrepancies exist between the text of the statistical analysis as planned in the protocol and the final SAP, the final SAP will define the planned analysis of record.

14.1. TRIAL ENDPOINTS

14.1.1. Safety Endpoints

The safety endpoints as measured throughout the long-term dosing of weekly TransCon hGH treatment include the following:

- Incidence of AEs
- Incidence of antibodies against hGH, including neutralizing antibodies
- Incidence of antibodies against PEG
- Incidence of antibodies against TransCon hGH
- Incidence of IGF-1 SDS > 2.0, > 3.0
- Parameters of HbA1c and lipids
- Hormone levels, including thyroid status and morning cortisol
- All other hematology and chemistry parameters
- Vital sign measurements

14.1.2. Efficacy Endpoints

The efficacy endpoints of long-term weekly TransCon hGH treatment include the following:

- Annualized HV
- Δ HSDS
- Proportion of subjects with IGF-1 SDS of 0 to +2.0. Additionally, cut points of -2.0 to +2.0 and -1.0 to +2.0 will be assessed.
- IGF-1 SDS

- IGFBP-3 SDS

14.1.3. Pharmacodynamic Endpoint

- Serum IGF-1 SDS at 5 days \pm 1-day post-dose

14.1.4. Other Endpoints

- Preference for weekly TransCon hGH or daily Genotropin treatment
- Satisfaction with weekly TransCon hGH
- Comfort, ease-of-use, and safety in subjects using the GH Auto-Injector

14.2. SAMPLE SIZE DETERMINATION

This trial is intended to assess long-term safety and efficacy in support of market approval. All subjects who have completed a prior phase 3 TransCon hGH trial, have not permanently discontinued investigational product, and meet eligibility criteria will be invited to participate. The sample size is determined by the prior trial sizes.

14.3. ANALYSIS POPULATIONS

The analysis population includes all subjects who receive at least one dose of investigational product.

14.4. STATISTICAL ANALYSES

Baseline and demographic data will be summarized to characterize the study population. Subgroups of interest, such as prior exposure to hGH and age categories, will be determined and corresponding subgroup analyses for safety and efficacy will be performed as appropriate. Prior and concomitant medication, as well as exposure of investigational product, will be summarized.

Data from clinical assessments will be summarized using descriptive statistics. Numerical variables will be summarized by mean, median, standard deviation, minimum, and maximum while categorical variables will be summarized by counts and proportions.

15. TRIAL CONDUCT

15.1. SITE INITIATION

Prior to participation, investigational sites and investigators will be evaluated for continued appropriate qualifications and ability to execute the trial. Each investigational site must undergo appropriate training on the trial protocol and ancillary trial procedures and documents through participation in a Site Initiation Visit (SIV) or Investigator Meeting (IM). Protocol and GCP training must take place before any subjects are enrolled at a site. SIVs and IMs will include, but may not be limited to, investigational product preparation and administration procedures, data collection requirements, and subject eligibility requirements.

15.2. SCREEN FAILURES

Screen failures are not expected because there is no screening period in this trial.

15.3. MAINTENANCE OF ENROLLMENT LOGS

Procedures for maintenance of enrollment logs are discussed in the trial manual.

15.4. DATA HANDLING AND RECORD KEEPING

15.4.1. Collection of Data

Data will be collected in the eCRF. The eCRF is an integral part of the trial and subsequent reports. It must be used to capture all trial-specific data collected and must be kept current to reflect subject status during the course of the trial. Only a Subject Identification Number will be used to identify the subject. The investigator must keep a separate subject identification code list with subject names and medical record numbers (or other personal identifiers).

The trial will use an Internet-based remote data entry system to collect clinical trial data at the investigational sites. The system complies with 21 CFR Part 11 and ICH E6 GCP. The system will be used to enter, modify, maintain, archive, retrieve, and transmit data. The system is configured based on the requirements from the Sponsor. Source documents are to be retained to enable a reconstruction and evaluation of the trial. Source documents include the hospital files and trial worksheets provided by the Sponsor. Data will be recorded in the trial worksheets as appropriate to complete and/or clarify the source data.

The design of the computerized system complies with all the applicable regulatory requirements for record keeping and record retention in clinical trials (21 CFR Part 11 and ICH E6 GCP) to the same degree of confidence as is provided with paper systems. Clinical investigators must retain either the original or a certified copy of all source documents sent to the Sponsor or its representatives, including query resolution correspondence. The system is designed so that changes to any record do not obscure the original information. The audit record clearly indicates that a change was made and clearly provides a means to locate and read the prior information. All changes to the data have an electronic audit trail, in accordance with 21 CFR 11.10(e). Electronic signatures will be used in conformance with 21 CFR Part 11.

